8.11.4.1 Safety Follow-up Visit

The mandatory Safety Follow-up Visit should be conducted approximately 30 days after the last dose of study intervention or before initiation of a new anticancer treatment, whichever comes first.

Participants who are eligible for retreatment with MK-1308A or pembrolizumab monotherapy may have up to 2 safety follow-up visits: 1 after the Initial Treatment or First Course and 1 after the Second Course.

8.11.4.2 Efficacy Follow-up Visits

Participants who complete the protocol-required cycles of study intervention or who discontinue study intervention for a reason other than disease progression will begin Efficacy Follow-up and should be assessed by continued tumor imaging every Q9W to monitor disease status. Every effort should be made to collect information regarding disease status until the start of new anticancer therapy, disease progression, death, end of study, or if the participant begins retreatment as detailed in Section 6.6. Information regarding poststudy anticancer treatment will be collected if new treatment is initiated. Participants who completed all efficacy assessments and/or will not have further efficacy assessments must enter Survival Follow-up.

Participants who are eligible to receive retreatment according to the criteria in Section 6 will move from Efficacy Follow-up to Second Course when they experience disease progression. Details are provided in the SoA (Section 1.3) for retreatment.

8.11.4.3 Survival Follow-up Contacts

Participant survival follow-up status will be assessed approximately every 12 weeks to assess for survival status until death, withdrawal of consent, or the end of the study, whichever occurs first.

The first survival follow-up assessment should be scheduled as described below:

1. For participants who discontinue treatment intervention and who will not enter Efficacy Follow-up, the first survival follow-up contact will be scheduled 12 weeks after the End of Treatment Visit and/or Safety Follow-up Visit (whichever is last).
2. For participants who completed assessments in Efficacy Follow-up due to progressive disease, the first survival follow-up contact will be scheduled 12 weeks after the last efficacy assessment follow-up visit has been performed.

8.11.5 Vital Status

To ensure current and complete survival information (vital status) is available at the time of database locks, updated vital status may be requested during the study by the Sponsor. For example, updated vital status may be requested before but not limited to, a DMC review, interim and/or final analysis. Upon Sponsor notification, all participants who do not/will not have a scheduled study visit or study contact during the Sponsor-defined period will be contacted for their vital status.

If a participant withdraws consent, vital status (survival information) may be obtained by review of public records, in accordance with local regulations. If a participant is lost to follow-up, vital status (survival information) can be conducted by review of medical records or public records when vital status is in question in accordance with local regulations.

9 STATISTICAL ANALYSIS PLAN

This section outlines the statistical analysis strategy and procedures for the study. Changes to analyses made after the protocol has been finalized will be documented in an sSAP and referenced in the CSR for the study. Post hoc exploratory analyses will be clearly identified in the CSR.

CCI [REDACTED]

9.1 Statistical Analysis Plan Summary

Key elements of the statistical analysis plan are summarized below; the comprehensive plan is provided in Sections 9.2-9.12.

Study Design Overview	A Phase 2, Multicenter, Multi Arm, Study to Evaluate MK-1308A (Coformulated quavonlimab (MK-1308)/pembrolizumab) Versus Other Treatments in Participants with Microsatellite Instability-High (MSI-H) or Mismatch Repair Deficient (dMMR) Stage IV Colorectal Cancer: (MK-1308A-008)
Treatment Assignment	
Cohort A: Approximately CCI participants will be randomized in a 1:1 ratio between 2 treatment groups: MK-1308A arm; Pembrolizumab monotherapy arm.
 
Cohort B: Approximately CCI participants will be randomized in a 1:1:1:1:1 ratio among 5 treatment groups: MK-1308A, MK-4280A, MK-7684A, MK-4830+pembrolizumab and pembrolizumab monotherapy arm.
 
Stratification factor for Cohorts A and B is RAS status (mutant vs WT).
 
This is an open-label study.

Analysis Populations	
Efficacy: ITT population
 
Safety: APaT

Primary Endpoint(s)	ORR as assessed by BICR per RECIST 1.1
Key Secondary Endpoint(s)	DOR as assessed by BICR per RECIST 1.1
Statistical Methods for Key Efficacy Analyses	
For each cohort:
 
The stratified M&N method [Miettinen, O. and Nurminen, M. 1985] will be used for comparison of ORR between arms.
 
The point estimate of ORR will be provided, together with 95% CI using exact binomial method proposed by Clopper and Pearson (1934) [Clopper, C. J. and Pearson, E. S. 1934].
 
The nonparametric Kaplan-Meier method will be used to estimate the DOR (if sample size permits).

Statistical Methods for Key Safety Analyses	Cohorts A and B: For analyses in which 95% CIs will be provided for between treatment differences in the percentage of participants with events, these analyses will be performed using the M&N method [Miettinen, O. and Nurminen, M. 1985].
Interim Analyses	CCI [REDACTED]
Multiplicity	CCI [REDACTED]
Sample Size and Power	
The planned sample size is approximately 320 participants.
 
Cohort A: The planned sample size is approximately CCI participants.
 
Cohorts B: The planned sample size is approximately CCI participants.
 
CCI [REDACTED]

9.2 Responsibility for Analyses/In-house Blinding

The statistical analysis of the data obtained from this study will be the responsibility of the Clinical Biostatistics department of the Sponsor.

This study is being conducted as an open-label study, ie, participant, investigators, and Sponsor personnel will be aware of participant treatment assignments after each participant is enrolled and treatment is assigned.

The Clinical Biostatistics department will generate the randomized allocation schedule(s) for study treatment assignment.

9.3 Hypotheses/Estimation

Objectives and hypotheses of the study are stated in Section 3.

9.4 Analysis Endpoints

Efficacy and safety endpoints that will be evaluated are listed below.

9.4.1 Efficacy Endpoints

Primary

- **Objective Response Rate**

The ORR is defined as the percentage of participants who achieve a confirmed CR or PR per RECIST 1.1 as assessed by BICR.

Secondary

- **Duration of Response**

For participants who demonstrate confirmed CR or PR, duration of response is defined as the time from the first documented evidence of CR or PR until disease progression or death due to any cause, whichever occurs first.

- **Progression-Free Survival**

The PFS is defined as the time from randomization to the first documented disease progression per RECIST 1.1 or death due to any cause, whichever occurs first.

- **Overall Survival**

OS is defined as the time from randomization to death due to any cause.

- **Objective Response Rate**

The ORR is defined as the percentage of participants who achieve a confirmed CR or PR per RECIST 1.1 as assessed by the investigator.

9.4.2 Safety Endpoints

Safety and tolerability will be assessed by clinical review of all relevant parameters, including AEs, SAEs, fatal AEs, laboratory tests, and vital signs. Furthermore, specific events will be collected and designated as ECIs as described in Section 8.4.7.

9.4.3 PRO Endpoints

CCI

9.5 Analysis Populations

9.5.1 Efficacy Analysis Populations

The ITT population will serve as the primary population for the analysis of efficacy data in this cohort. The ITT population consists of all randomized participants. Participants will be analyzed in the treatment arm to which they are randomized. Details of the approach to handling missing data are provided in Section 9.6.1.5.

9.5.2 Safety Analysis Populations

Safety analyses will be conducted in the APaT population for each cohort, which consists of all randomized participants who received at least one dose of study treatment. Participants will be included in the treatment group corresponding to the study treatment they actually received for the analysis of safety data using the APaT population. This will be the treatment group to which they are randomized except for participants who take incorrect study treatment for the entire treatment period; such participants will be included in the treatment group corresponding to the study treatment actually received.

At least one laboratory or vital sign measurement obtained subsequent to at least one dose of study treatment is required for inclusion in the analysis of the respective safety parameter. To assess change from baseline, a baseline measurement is also required.

9.5.3 PRO Analysis Populations

CCI

9.6 Statistical Methods

This section describes the statistical methods that address the primary and secondary objectives. Methods related to exploratory objectives will be described in the sSAP.

9.6.1 Statistical Methods for Efficacy Analyses

Efficacy analyses will be conducted for each cohort separately. The stratification factor used for randomization (see Section 6.3.2) will be applied to all stratified analyses.

9.6.1.1 Objective Response Rate (ORR)

The stratified M&N method [Miettinen, O. and Nurminen, M. 1985] will be used for comparison of the ORR between arms.

The point estimate of ORR will be provided by treatment group and cohort, together with 95% CI using exact binomial method proposed by Clopper and Pearson (1934) [Clopper, C. J. and Pearson, E. S. 1934].

9.6.1.2 Duration of Response (DOR)

The nonparametric Kaplan-Meier method will be used to estimate the DOR curve if sample size permits, and median estimate from the Kaplan-Meier curve will also be provided. Only the subset of participants who show a confirmed CR or PR will be included in this analysis.

Censoring rules for DOR are summarized in [Table 9](#).

Table 9 Censoring Rules for DOR

Situation	Date of Progression or Censoring	Outcome
No progression nor death, no new anticancer therapy initiated	Last adequate disease assessment	Censor (non-event)
No progression nor death, new anticancer therapy initiated	Last adequate disease assessment before new anticancer therapy initiated	Censor (non-event)
Death or progression immediately after ≥ 2 consecutive missed disease assessments or after new anticancer therapy, if any	Earlier date of last adequate disease assessment prior to ≥ 2 missed adequate disease assessments and new anticancer therapy, if any	Censor (non-event)
Death or progression after ≤ 1 missed disease assessments and before new anticancer therapy, if any	PD or death	End of response (Event)
DOR=duration of response; PD=progressive disease. A missed disease assessment includes any assessment that is not obtained or is considered inadequate for evaluation of response.		

9.6.1.3 Progression-Free Survival (PFS)

The nonparametric Kaplan-Meier method will be used to estimate the PFS curve, and median estimate from the Kaplan-Meier curve will also be provided. The stratified Cox proportional hazard model with Efron's method of tie handling will be used to assess the magnitude of the treatment difference (ie, hazard ratio) between the treatment arms. The hazard ratio and its 95% CI from the stratified Cox model with a single treatment covariate will be reported.

Since disease progression is assessed periodically, PD can occur any time in the time interval between the last assessment where PD was not documented and the assessment when PD is documented. The true date of disease progression will be approximated by the earlier of the date of the first assessment at which PD is objectively documented per RECIST 1.1 by BICR and the date of death. Death is always considered a PD event.

For PFS analysis, any participant who experiences an event (PD or death) immediately after 2 or more missed disease assessments will be censored at the last disease assessment prior to the missed visits. In addition, any participant who initiates new anticancer therapy will be censored at the last disease assessment prior to the initiation of new anticancer therapy. Participants who do not start new anticancer therapy and who do not experience an event will be censored at the last disease assessment. If a participant meets multiple criteria for censoring, the censoring criterion that occurs earliest will be applied. The censoring rules for the PFS analysis are summarized in [Table 10](#).

Table 10 Censoring Rules for PFS

Situation	Primary Analysis
PD or death documented after ≤ 1 missed disease assessment, and before new anticancer therapy, if any	Progressed at date of documented PD or death
Death or progression immediately after ≥ 2 consecutive missed disease assessments, or after new anticancer therapy	Censored at last disease assessment prior to the earlier date of ≥ 2 consecutive missed disease assessment and new anticancer therapy, if any
No PD and no death; and new anticancer treatment is not initiated	Censored at last disease assessment
No PD and no death; new anticancer treatment is initiated	Censored at last disease assessment before new anticancer treatment
PD=progressive disease; PFS=progression-free survival.	

9.6.1.4 Overall Survival (OS)

The nonparametric Kaplan-Meier method will be used to estimate the survival curve, and median estimate from the Kaplan-Meier curve will also be provided. For Cohort A, a stratified Cox proportional hazard model with Efron's method of tie handling will be used to assess the magnitude of the treatment difference (ie, hazard ratio) between the treatment arms. The hazard ratio and its 95% CI from the stratified Cox model with a single treatment covariate will be reported.

Participants without documented death at the time of analysis will be censored at the date the participant was last known to be alive.

9.6.1.5 Analysis Strategy for Key Efficacy Variables

A summary of the primary analysis strategy for the key efficacy endpoints is provided in [Table 11](#).

Table 11 Analysis Strategy for Key Efficacy Variables

Endpoint/Variable	Statistical Method	Analysis Population	Missing Data Approach
Primary Analyses			
ORR per RECIST 1.1 by BICR	Stratified Miettinen and Nurminen method Summary statistics with 95% CI using Exact method based on binomial distribution	Cohorts A and B: ITT	Participants with missing data are considered non-responders
Secondary Analyses			
DOR per RECIST 1.1 by BICR	Summary statistics using Kaplan-Meier method	Cohorts A and B: All Responders	Censored according to rules in Table 9
PFS per RECIST 1.1 by BICR	Estimation: Stratified Cox model with Efron's tie handling method Summary statistics using Kaplan-Meier method	Cohorts A and B: ITT	Censored according to rules in Table 10
OS	Estimation: Stratified Cox model with Efron's tie handling method Summary statistics using Kaplan-Meier method	Cohorts A and B: ITT	Censored at the date participant last known to be alive
BICR=blinded independent central review; CI=confidence interval; DOR=Duration of Responses; ITT=intention-to-treat population; M&N=Miettinen & Nurminen; ORR=objective response rate; OS=overall survival; PFS=progression-free survival; RECIST 1.1=Response Evaluation Criteria in Solid Tumors.			

9.6.2 Statistical Methods for Safety Analyses

Safety and tolerability will be assessed by clinical review of all relevant parameters including AEs, laboratory tests and vital signs. Safety analyses will be conducted for each cohort separately.

The analysis of safety results will follow a tiered approach ([Table 12](#)). The tiers differ with respect to the analyses that will be performed. AEs (specific terms as well as system organ class terms) and events that meet predefined limits of change in laboratory and vital signs are either prespecified as “Tier 1” endpoints or will be classified as belonging to “Tier 2” or “Tier 3” based on observed proportions of participants with an event.

Tier 1 Events

CCI

CCI

Tier 2 Events

Tier 2 parameters will be assessed via point estimates with 95% CIs provided for differences in the proportion of participants with events using the M&N method, an unconditional, asymptotic method [Miettinen, O. and Nurminen, M. 1985].

Membership in Tier 2 requires that at least 10% of participants in any treatment group exhibit the event; all other AEs and predefined limits of change will belong to Tier 3. The threshold of at least 10% of participants was chosen for Tier 2 events because the population enrolled in this study is in critical condition and usually experiences various AEs of similar types regardless of treatment; events reported less frequently than 10% of participants would obscure the assessment of the overall safety profile and add little to the interpretation of potentially meaningful treatment differences. In addition, Grade 3 to 5 AEs ($\geq 5\%$ of participants in 1 of the treatment groups) and SAEs ($\geq 5\%$ of participants in 1 of the treatment groups) will be considered Tier 2 endpoints. Because many 95% CIs may be provided without adjustment for multiplicity, the CIs should be regarded as a helpful descriptive measure to be used in safety review, not as a formal method for assessing the statistical significance of the between-group differences.

Tier 3 Events

Safety endpoints that are not Tier 1 or 2 events are considered Tier 3 events. The broad AE categories consisting of the proportion of participants with any AE, a drug-related AE, a serious AE, an AE which is both drug-related and serious, a Grade 3-5 AE, a drug-related Grade 3-5 AE, and discontinuation due to an AE will be considered Tier 3 endpoints. Only point estimates by treatment group are provided for Tier 3 safety parameters.

For continuous measures such as changes from baseline in laboratory and vital sign parameters, summary statistics for baseline, on-treatment, and change from baseline values will be provided by treatment group in table format.

Table 12 Analysis Strategy for Safety Parameters

Safety Tier	Safety Endpoint	95% CI for Treatment Comparison	Descriptive Statistics
[Redacted]			

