2.3 Benefit/Risk Assessment

Pembrolizumab monotherapy has shown significant activity in the setting of dMMR/MSI-H mCRC in both first line and later settings. However, the benefit is not universal; in the KEYNOTE-177 study approximately 40% of participants showed disease progression soon after beginning treatment.

The addition of a CTLA-4 antibody (ie, ipilimumab), in an uncontrolled dMMR/MSI-H cohort, has appeared to increase the effectiveness of immunotherapeutic approaches against these tumors. Participants with dMMR/MSI-H CRC treated with both CTLA-4 and PD-1 inhibition had a response rate of 62% and 12-month PFS of 76% [Lenz, H. J., et al 2020] whereas pembrolizumab monotherapy had a response rate of 44% and 12-month PFS of 55% [Andre, T., et al 2020]. However, these approaches have never been directly compared, which is the goal of this study.

The existing preclinical and early clinical data suggest that inhibiting other immune checkpoint molecules in combination with PD-1 blockade is a promising therapeutic strategy and that the risk/benefit assessment for participants in this study will be favorable.

Phase 1 studies have shown that MK-4830 and MK-7684 as monotherapy or in combination with pembrolizumab can potentially enhance antitumor efficacy in patients with solid tumors (refer to respective IBs and Section 2.1). Also, preliminary results support the use of MK-1308 and MK-4280 in combination with pembrolizumab (refer to respective IBs and Section 2.1). An advantage of the platform study design is that it will allow rapid, concurrent evaluation of multiple investigational agents in chemotherapy refractory and previously untreated participants with metastatic dMMR/MSI-H CRC. This may identify new combination interventions with improved responses over those historically achieved with current treatment options. Therefore, a potential benefit may be faster clinical development of novel interventions benefiting this particular patient population, while reducing exposure of participants to interventions that do not show improved clinical benefit. Nevertheless, combination therapy might prove to have greater toxicity rates, particularly with respect to colitis and hepatitis. A goal of this study will be to formally assess AE and SAE rates.

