4.3 Justification for Dose

4.3.1 Justification of MK-1308A Dose

The dose composition and schedule of MK-1308A is 25 mg quavonlimab plus 400 mg pembrolizumab to be administered Q6W. This formulation and dosing regimen were chosen after data analyses of 215 participants in the MK-1308-001 study who were given varying dose levels of quavonlimab (25 mg, 75 mg, and 200 mg Q3W or Q6W) and a fixed dose of pembrolizumab (200 mg Q3W). Evaluation of the safety, tolerability, PK, pharmacodynamics, and efficacy data from this part of the study showed that 25 mg quavonlimab Q6W in combination with pembrolizumab Q3W was equally efficacious but safer than the 75 mg and 200 mg quavonlimab dose levels, thus the 25 mg Q6W dose regimen was chosen as the RP2D. Following the selection of the 25 mg Q6W regimen of quavonlimab, the 400 mg Q6W regimen of pembrolizumab was considered appropriate in the development of the pembrolizumab + quavonlimab fixed-dose coformulation (MK-1308A), given the approval of this regimen of pembrolizumab as a safe and efficacious alternative to the 200 mg Q3W regimen. Preliminary PK data collected from 29 participants in the MK-1308-001 study who were treated with MK-1308A showed similar exposures of quavonlimab compared with sequential administration and coadministration of quavonlimab and pembrolizumab. Further, the observed 400 mg Q6W pembrolizumab concentration data in combination with 25 mg Q6W quavonlimab are consistent and within the range of the simulated pembrolizumab monotherapy data at the same dose using the reference population PK model created from 2993 subjects. Analysis of ADA impact on the PK exposure of quavonlimab in combination with pembrolizumab to date show that anti-quavonlimab antibodies do generally reduce quavonlimab exposures in subjects who are ADA positive with higher S/N generally causing lower exposure. Pembrolizumab ADA formation has no impact on exposures of pembrolizumab in combination with quavonlimab. Details regarding PK and ADA data may be found in the quavonlimab, MK-1308A, and pembrolizumab IBs.

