4.3.2 Justification of Pembrolizumab Dose

The planned dose of pembrolizumab monotherapy for this study is 400 mg Q6W.

The 400 mg Q6W dosing regimen of pembrolizumab is approved for adult indications.

A 400 mg Q6W dosing regimen of pembrolizumab is expected to have a similar benefit-risk profile as 200 mg Q3W, in all treatment settings in which 200 mg Q3W pembrolizumab is currently appropriate [Lala, M., et al 2020]. Specifically, the dosing regimen of 400 mg Q6W for pembrolizumab is considered adequate based on M&S analyses, given the following rationale.

- PK simulations demonstrating that in terms of pembrolizumab exposures:
 C_{avg} (or AUC) at 400 mg Q6W is similar to the approved 200 mg Q3W dose, thus bridging efficacy between dosing regimens.

Trough concentrations (C_{min}) at 400 mg Q6W are generally within the range of those achieved with 2 mg/kg or 200 mg Q3W in the majority (>99%) of participants.

Peak concentrations (C_{max}) at 400 mg Q6W are well below the C_{max} for the highest clinically tested dose of 10 mg/kg Q2W, supporting that the safety profile for 400 mg Q6W should be comparable to the established safety profile of pembrolizumab.
- Exposure-response for pembrolizumab has been shown to be flat across indications, and OS predictions in melanoma and NSCLC show that efficacy at 400 mg Q6W is expected to be similar to 200 mg or 2 mg/kg Q3W, given the similar exposures; thus, 400 mg Q6W is expected to be efficacious across indications.

When administered in combination with MK-4830 (Section 4.3.5), the planned dose of pembrolizumab is 200 mg Q3W.

The dosage of pembrolizumab for participants who received Q3W dosing in closed arms and who elect to transition to pembrolizumab monotherapy is 200 mg Q3W.

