6.1 Study Intervention(s) Administered

The study intervention(s) to be used in this study are outlined in [Table 5](#).

All products indicated in [Table 5](#) will be provided centrally by the Sponsor.

For any commercially available product that is provided by the study site, subsidiary, or designee, every attempt will be made to source these supplies from a single lot/batch number.

Refer to Section 8.1.9 for details regarding administration of the study intervention.

Table 5 Study Interventions

Arm Name	Arm Type	Intervention Name	Intervention Type	Dose Formulation	Unit Dose Strength(s)	Dosage Level(s)	Route of Administration	Regimen/ Treatment Period/ Vaccination Regimen	Use	IMP or NIMP/ AxMP	Sourcing
Cohorts A and B: Pembrolizumab monotherapy	Active Comparator	Pembrolizumab	Biological/Vaccine	Solution	25 mg/mL	400 mg	IV Infusion	Q6W up to 17 doses	Comparator	IMP	Centrally by Sponsor
Cohorts A and B: MK-1308A	Experimental	MK-1308A	Biological/Vaccine	Solution	quavonlimab 25 mg + pembrolizumab 400 mg/ 17.5 mL vial	25 mg/ 400 mg	IV Infusion	Q6W up to 17 doses	Test Product	IMP	Centrally by Sponsor
Cohort B: MK-4280A	Experimental	MK-4280A	Drug	Solution	20 mg/mL favezelimab + 5 mg/mL pembrolizumab for a total of 25 mg/mL	800 mg MK-4280 + 200 mg MK-3475	IV Infusion	Q3W up to 35 doses	Test Product	IMP	Centrally by Sponsor
Cohort B: MK-7684A	Experimental	MK-7684A	Biological/Vaccine	Solution	vibostolimab 10 mg/mL + pembrolizumab 10 mg/mL	200 mg MK-7684 + 200 mg MK-3475	IV Infusion	Q3W up to 35 doses	Test Product	IMP	Centrally by Sponsor

Arm Name	Arm Type	Intervention Name	Intervention Type	Dose Formulation	Unit Dose Strength(s)	Dosage Level(s)	Route of Administration	Regimen/ Treatment Period/ Vaccination Regimen	Use	IMP or NIMP/ AxMP	Sourcing
Cohort B: MK-4830 + Pembrolizumab	Experimental	MK-4830 + Pembrolizumab	Biological/Vaccine	Solution	MK-4830 50 mg/mL + pembrolizumab 25 mg/mL	800 mg MK-4830 + 200 mg MK-3475	IV Infusion	Q3W up to 35 doses	Test Product	IMP	Centrally by Sponsor
Cohort B: Participants who received Q3W dosing in closed arms	Active Comparator	Pembrolizumab	Biological/Vaccine	Solution	25 mg/mL	200 mg	IV Infusion	Q3W up to a total of 35 doses including doses received as part of closed arm	Comparator	IMP	Centrally by Sponsor or locally

AxMP = auxiliary medicinal product; EEA =European Economic Area; IMP=investigational medicinal product; IV=intravenous; NIMP=noninvestigational medicinal product; Q3W= every 3 weeks; Q6W= every 6 weeks.

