6.1.1 Treatment

6.1.1.1 Initial Treatment or First Course

The Initial Treatment or First Course of MK-1308A or pembrolizumab monotherapy consists of up to 17 treatments of Q6W therapy. The Initial Treatment or First Course of MK-4280A, MK-7684A, or MK-4830 plus pembrolizumab consists of up to 35 treatment cycles of Q3W therapy. Note: The number of treatments is calculated starting with the first dose.

Participants may be eligible for Second Course described in Section 6.1.1.2.

In the event of a study arm being closed, the Sponsor may offer investigators the option of continuing study treatment with pembrolizumab monotherapy or continuing the assigned study treatment to participants who are receiving clinical benefit. At implementation of Amendment 05, the following treatment arms are considered closed: Cohort B: MK-4280A, Cohort B: MK-7684A, and Cohort B: MK-4830+pembrolizumab.

As of the Investigator Letter dated 16-DEC-2024, participants who were receiving MK-4280A were offered the option to continue study therapy until treatment completion or transition to pembrolizumab monotherapy, and participants who were receiving MK-7684A were discontinued from that study therapy and offered the option to transition to pembrolizumab monotherapy. As per the Investigator Letter dated 25-SEP-2023, the MK-4830+pembrolizumab arm was closed to enrollment; all ongoing participants were offered the option to continue study therapy until treatment completion or transition to pembrolizumab monotherapy. For participants who elect to transition to pembrolizumab monotherapy, the dosage would be 200 mg Q3W up to a total of 35 doses including doses received as part of closed arm.

Participants in closed arms with access to approved SOC (eg, immunotherapy, chemotherapy, targeted therapy) should be considered for discontinuation from the study. Participants in closed arms who are benefiting from pembrolizumab monotherapy, but unable to access it as SOC outside the study, may continue on study and receive treatment with pembrolizumab monotherapy until discontinuation criteria are met. The final required study visit will be the Safety Follow-up Visit.

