6.3 Measures to Minimize Bias: Randomization and Blinding

6.3.1 Intervention Assignment

Intervention allocation will occur centrally using an IRT system. There are 7 study intervention arms. Participants in Cohort A will be assigned randomly in a 1:1 ratio to MK-1308A or pembrolizumab monotherapy, respectively. Participants in Cohort B will be assigned randomly in a 1:1:1:1:1 ratio to MK-1308A, pembrolizumab monotherapy, MK-4280A, MK-7684A, or MK-4830+pembrolizumab, respectively.

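### A supplementary cohort-stratified safety comparison of MK-1308A with pembrolizumab would narrow the Tier 2 intervals at little cost

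*Combined protocol and SAP*

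**What the plan says.** Section 9.6.2 sets a general rule ahead of the tier definitions: "Safety analyses will be conducted for each cohort separately". Section 9.6.1 has the parallel rule for efficacy.

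The regimens do not differ by cohort. Table 5 (Section 6.1) uses one row for "Cohorts A and B: MK-1308A" and one for pembrolizumab monotherapy in the same two cohorts. The supporting sections agree:

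- Section 4.3.1: "The dose composition and schedule of MK-1308A is 25 mg quavonlimab plus 400 mg pembrolizumab to be administered Q6W".
- Section 4.3.2: "The planned dose of pembrolizumab monotherapy for this study is 400 mg Q6W".
- Section 6.1.1.1: "The Initial Treatment or First Course of MK-1308A or pembrolizumab monotherapy consists of up to 17 treatments of Q6W therapy".

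On allocation, Section 6.3.1 states: "Participants in Cohort A will be assigned randomly in a 1:1 ratio to MK-1308A or pembrolizumab monotherapy, respectively". Cohort B is randomized 1:1:1:1:1 over five arms that include both of these, so the two are again 1:1 to each other.

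Tier 2 covers events in at least 10% of any treatment group, plus Grade 3 to 5 AEs and SAEs in at least 5% of a group. These get a Miettinen-Nurminen 95% CI for the difference, which the section describes as descriptive and unadjusted. Broad categories, including any Grade 3-5 AE, are Tier 3 and get point estimates by group only.

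**The concern.** The same randomized contrast is run twice, in two separately randomized cohorts, and the visible plan never puts the two results together. Section 2.3 raises the possibility of greater toxicity with combination therapy, naming colitis and hepatitis, and adds: "A goal of this study will be to formally assess AE and SAE rates". After the closures recorded in Amendment 05, MK-1308A is the only experimental regimen still open. With about 320 participants planned over seven arms, each single-cohort comparison is small.

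What is at stake is precision. A safety reviewer looking at an individual Tier 2 term gets two wide intervals, although the existing data would support a narrower one that still compares participants only within their own cohort.

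**Working it through.** The documents give no precision figure for safety, so there is nothing of the plan's own to reproduce. The check is how much narrower a cohort-stratified interval would be.

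**Inputs**
- Planned total of about 320 (Section 9.9), with two arms in Cohort A and five in Cohort B (Section 6.3.1).
- Cohort sizes are redacted. With *a* and *b* as the per-arm sizes in A and B, planned equal allocation implies 2*a* + 5*b* = 320. An even split is 320/7 = 45.7 per arm.
- Illustrative event rates of 22% v 32%. The 22% is the Grade 3+ rate that Section 2.1 quotes for pembrolizumab in the untreated setting; the 32% is an assumption. With equal rates in both cohorts the percentage reductions do not depend on these values.

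**Formula.** The standard error of a difference is √([p0(1−p0) + p1(1−p1)]/n). With equal rates in both cohorts, the stratified estimate behaves as if n = *a* + *b* per arm. The reduction in CI width is therefore
- against Cohort A alone: 1 − √(*a*/(*a*+*b*))
- against Cohort B alone: 1 − √(*b*/(*a*+*b*))

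**Results**

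| Per arm, A / B | Cohort totals, A / B | Narrower than A alone | Narrower than B alone |
|---|---|---|---|
| 30 / 52 | 60 / 260 | 39.5% | 20.4% |
| 40 / 48 | 80 / 240 | 32.6% | 26.1% |
| 45.7 / 45.7 | even split | 29.3% | 29.3% |
| 50 / 44 | 100 / 220 | 27.1% | 31.6% |
| 60 / 40 | 120 / 200 | 22.5% | 36.8% |
| 80 / 32 | 160 / 160 | 15.5% | 46.5% |

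Against the more precise cohort the reduction runs from 15.5% to 29.3%; against the other, from 29.3% to 46.5%. The even-split value is 1 − 1/√2 = 29.3%.

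In points, at the even split: 0.22×0.78 + 0.32×0.68 = 0.3892. The half-width is 1.96√(0.3892/45.7) = 18.1 points for one cohort and 1.96√(0.3892/91.4) = 12.8 points combined.

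**Check with the plan's own interval method.** For a hypothetical event in 17/46 v 10/46, the Miettinen-Nurminen 95% CI is −3.5 to +33.2 points, a width of 36.7. With the same counts in both cohorts, the cohort-stratified interval is +2.0 to +28.0, a width of 26.0. The ratio 26.0/36.7 = 0.71 agrees with the formula.

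**Unequal background rates.** Suppose one cohort has 14/46 v 7/46 (−2.1 to +32.1, width 34.2) and the other 17/46 v 10/46 (width 36.7). The stratified interval is +2.5 to +27.6, a width of 25.1. That is 1 − 25.1/34.2 = 27% and 1 − 25.1/36.7 = 32% narrower than the two single-cohort intervals. Only the widths matter here; no weight is placed on whether zero lies inside an interval.

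**The case against.** By-cohort analysis follows the plan's own structure. The safety objectives in Section 3 are written separately for Cohorts A and B. The populations differ (chemotherapy refractory v untreated). So does safety contact: Cohort B participants on a Q6W regimen have a Day 22 visit in every cycle (Section 8.11.2), whereas Table 1 schedules Day 22 for Cohort A in Cycles 1 and 2 only. A combined figure answers a question that no listed objective asks. All of this stands, and it makes the plan's choice legitimate. It argues against crude pooling and against replacing the cohort tables. It does not argue against a stratified supplement, in which each comparison stays within its own randomization and visit schedule.

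Three further points also stand and limit the claim:

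- **Grade 3-5 AEs.** A reader might infer that cohort-only intervals are too wide to show a rise in Grade 3-5 AEs overall. The plan produces no between-arm interval for that category, because it is Tier 3. The precision argument applies to Tier 2 terms.
- **Power.** A reader might turn the narrower interval into a chance of excluding zero. Section 9.6.2 disclaims using these intervals to assess statistical significance, and no safety alpha, power or margin is visible.
- **Redaction.** The Tier 1 text, Table 12 and part of the opening of Section 9 are blacked out, so it cannot be said that the plan contains no combined analysis anywhere. The rule quoted from Section 9.6.2 is nevertheless general and visible.

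**Conclusion.** The point holds as a missed efficiency, not an error or a contradiction. The same two regimens are randomized 1:1 to each other in both cohorts, and the visible text analyses their safety only within cohort. For splits from 30/52 to 80/32 per arm and equal event rates, a cohort-stratified interval would be about 15 to 29% narrower than the more precise cohort's and about 29 to 47% narrower than the other's.

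These figures rest on assumed cohort sizes, since both are redacted, and on planned equal allocation; the early closure of the MK-4830 arm to enrollment could shift the actual sizes.

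A reader might infer that the plan discards a fixed 29% of the available precision. The documents do not support that: 29% needs equal per-arm sizes and equal rates, and all treated participants are still tabulated within their cohort. Nor do they single out this comparison as the principal safety contrast. The parallel efficacy rule, "Efficacy analyses will be conducted for each cohort separately", might suggest that ORR should be combined too. The safety argument does not extend to that, and no change to the efficacy analysis is proposed.

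**What to change.** Keep the cohort-specific tables as the primary safety presentation. Add to Section 9.6.2 one pre-specified supplementary comparison of MK-1308A with pembrolizumab monotherapy across Cohorts A and B for Tier 2 events:

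- Use the Miettinen-Nurminen method stratified by cohort, not crude pooling, and restrict it to these two arms.
- Show the cohort-specific differences beside the combined one.
- Repeat that the intervals are descriptive.
- State how the 10% and 5% Tier 2 thresholds apply when an event qualifies in one cohort only.

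If between-arm intervals are also wanted for broad categories such as any Grade 3-5 AE, say explicitly that this departs from the Tier 3 rule of point estimates only.

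The cost is a short piece of SAP wording, which could go in the sSAP that Section 9 provides for, and one more table set. No new data are needed. The downside is that the combined figure is an average if the true difference varies by cohort, which is why the cohort results stay alongside.
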